7.1.5 Assessment of Concomitant Medications/Treatments other than the Investigational Product

Restrictions for prior and concomitant medications and therapies are provided in Section 5.1.1 and Section 5.1.2. Prior and concomitant medications and therapies will be coded using the latest version of the World Health Organization Drug Dictionary.

7.1.5.1 Prior Medications

Information regarding prior medications taken by the subject within the 30 days before signing the ICF will be recorded in the subject's eCRF.

7.1.5.2 Concomitant Medications

The Investigator is responsible for ensuring that details regarding the medication are adequately recorded in the subject's source documents and in the eCRF. Medication information will be recorded at the Screening visit for the prior 30 days and at Day -1. At each follow-up study visit, new concomitant medication and changes to existing medications will be recorded. Any concomitant medication deemed necessary for the welfare of the subject during the study may be given at the discretion of the Investigator. If a concomitant medication is taken, except for those specified in the protocol, a joint decision will be made by the Investigator and the Sponsor to continue or discontinue the subject based on the time the medication was administered, its pharmacology and PK, and whether the use of the medication will compromise the safety of the subject or the interpretation of the data.

7.2 **Laboratory Evaluations**

7.2.1 **Clinical Laboratory Evaluations**

The following clinical laboratory assessments will be performed at the time points indicated in the schedule of events (Section 17.1):

Absolute neutrophil count, hemoglobin, platelet count, and white Hematology

blood cell count

Alanine aminotransferase, albumin^(a), alkaline phosphatase, aspartate Serum Chemistry

aminotransferase, bicarbonate^(b), blood urea nitrogen, calcium^(a), chloride^(b), creatinine^(c), glucose (fasted), potassium, sodium, and

total bilirubin

Coagulation^(a) Prothrombin time and activated partial thromboplastin time

Urinalysis Blood, glucose^(a), and protein

Serology (IgG)^(a) Hepatitis B surface antigen, hepatitis C virus antibody, and human

immunodeficiency virus antibody types 1 and 2

Flavivirus Screening

(IgM and IgG)^(a)

DENV antibody, Zika virus antibody (IgM only), and West Nile virus

antibody

Urine Drug Screen^(d) Amphetamines (includes methamphetamines and

ecstasy/methylenedioxymethamphetamine), barbiturates,

benzodiazepines, cannabinoids, cocaine metabolites, cotinine, ethyl alcohol, methadone, methamphetamines, opiates (including heroin,

codeine, and oxycodone/oxymorphone)

Pregnancy Test

(female subjects

Follicle-stimulating hormone, serum pregnancy test (human chorionic gonadotropin)

only)(e)

Abbreviations: IgG, immunoglobulin G; IgM, immunoglobulin M.

Note: Results of alanine aminotransferase, aspartate aminotransferase, alkaline phosphatase, blood urea nitrogen, creatinine, and total bilirubin that are below the reference ranges are acceptable and will not exclude participation.

(a) Clinical laboratory assessments will be performed at Screening and Check-in on Day -1 only, except serology and flavivirus screening will occur only at Screening.

(b) Bicarbonate and chloride will only be used for calculation of anion gap ([sodium + potassium] -[chloride + bicarbonate)]. Volunteers with an anion gap greater than the upper limit of normal at Screening and Check-in on Day –1 will be excluded from participation in the study.

(c) Volunteers with an estimated creatinine clearance (calculated using CKD-EPI method) <90 mL/min/1.73 cm² at Screening will be excluded from participation in the study.

(d) Urine drug screening will be performed at Screening, Check-in on Day -1, on Day 22 (±2), on Day 43 (±3), and on Day 85 (\pm 5) except cotinine screening will occur only on Day -1.

(c) For females in menses, screening urinalysis may be postponed or repeated, but a result should be available prior to Day 1.

Results of the absolute neutrophil count, hemoglobin, platelet count, white blood cell count, alanine aminotransferase, albumin, anion gap, aspartate aminotransferase, blood urea nitrogen, calcium, creatinine, creatinine clearance, glucose (fasting), potassium, sodium, prothrombin time and activated partial thromboplastin time, and urinalysis for blood, glucose, and protein must be normal at Screening and Check-in on Day –1 for eligibility. A repeat is allowed for out-of-range values, when not considered clinically significant by the Investigator, for the purpose of determining eligibility. The Investigator may choose to run addition clinical laboratory assessments at Screening or Check-in to assess volunteer eligibility to enroll. Results of these tests that fall outside of the reference ranges will be evaluated for inclusion into the study at the discretion of the Investigator.

Laboratory assessments for monitoring safety and determining dose escalation include absolute neutrophil count, hemoglobin, platelet count, white blood cell count, alanine aminotransferase, alkaline phosphatase, aspartate aminotransferase, anion gap, blood urea nitrogen, creatinine, glucose (fasted), potassium, sodium, and total bilirubin. Instruments will be programmed to only generate results for hematology (including % relative neutrophils used to calculate absolute neutrophil count) and chemistry tests (including chloride and bicarbonate used to calculate anion gap) used to monitor safety and dose escalation after enrollment. Results of % relative neutrophils, chloride and bicarbonate will not individually be reviewed for evaluation of dose escalation or study halting criteria.

Instruments will be programmed to only generate results for hematology and chemistry tests used to monitor safety and determining dose escalation include absolute neutrophil count, hemoglobin, platelet count, white blood cell count, alanine aminotransferase, anion gap, blood urea nitrogen, creatinine, glucose (fasted), potassium, sodium, and total bilirubin.

The clinical laboratory that performs the tests will provide the reference ranges for all clinical laboratory parameters. Clinical laboratory tests that are thought to be due to a laboratory error may be repeated once at the discretion of the Investigator for assessment of inclusion and exclusion criteria or evaluation of clinical laboratory abnormalities.

7.2.2 Pharmacokinetic Sampling

Blood samples for PK analysis of concentrations of AV-1 in serum will be collected predose (within 15 minutes) and at 0.5, 1 (end of infusion), 1.25, 1.5, 2, 3, 4, 6, 8, 12, 24 and 48 hours after the start of the infusion, on Day 5 prior to discharge, and at the follow-up visits on Days 8 (+2), 15 (\pm 2), 22 (\pm 2), 29 (\pm 2), 43 (\pm 3), 57 (\pm 3), 85 (\pm 5), and 120 (\pm 5) (or ET). A validated ECL ELISA method will be used to quantify AV-1 in serum samples for PK analyses as outlined in Section 10.4.3.

7.2.3 Anti-AV-1 Antibody Sampling

Blood samples for anti-AV-1 antibody analysis will be collected at Check-in (Day -1) and on Days 29 (± 2), 85 (± 5), and 120 (± 5) (or ET). A validated ECL ELISA method will be used for detection and confirmation of pre-existing and treatment-emergent anti-AV-1 antibodies in

serum samples based on the MesoScale Discovery platform that utilizes labeled AV-1 for detection of anti-AV-1 antibodies and treatment-emergent antibodies.

7.2.4 Hypersensitivity Testing

Subjects will be monitored closely for signs and symptoms of hypersensitivity during and following infusion of the IP. A blood sample will be collected for all subjects on Day -1 and tested only if a suspected hypersensitivity reaction occurs during or following IP infusion on Day 1 at the discretion of the Investigator in consultation with the Sponsor. The subject will be treated using the standard site procedures if a subject develops a suspected hypersensitivity reaction. At the discretion of the Investigator, an additional blood sample will be drawn as soon as possible after the event occurs (Day 1) and again the following day (Day 2). Hypersensitivity testing of the Day -1, Day 1, and Day 2 samples will only occur in the event of a suspected hypersensitivity reaction at the discretion of the Investigator and in consultation with the Sponsor. Refer to the manual of procedures for further details.

7.2.5 Laboratory Specimen Preparation, Handling, and Storage

Details for the collection, processing, and storage of samples for assessment of PK and anti-AV-1 antibody will be provided to the clinical unit separately and outlined in the laboratory manual.

7.2.6 Laboratory Specimen Shipping

Details for the shipping of samples for the assessment of PK and anti-AV-1 antibody will be provided to the clinical unit separately and outlined in the laboratory manual.

8 ASSESSMENT OF SAFETY

8.1 Assessing and Recording Safety Parameters

Subjects will be monitored throughout the duration of the study to assess safety of a single IV infusion of AV-1 as per the schedule of events (Section 17.1).

Safety assessments will include:

- Incidence and severity of AEs
- Incidence of SAEs
- Physical examinations
- Clinical safety laboratory tests
- Vital sign measurements
- 12-lead ECGs

8.1.1 Adverse Events

An AE is defined by ICH E6(R2) as any untoward medical occurrence in a patient or clinical investigation subject administered a pharmaceutical product regardless of its causal relationship to the study treatment. The FDA defines an AE as any untoward medical occurrence associated with the use of a drug in humans, whether or not considered drug related.

An AE can therefore be any unfavorable and unintended sign (including an abnormal laboratory finding), symptom, or disease temporally associated with the use of medicinal (investigational) product. The occurrence of an AE may come to the attention of study personnel during study visits and interviews of a study recipient presenting for medical care, or upon review by a study monitor.

All AEs, including solicited local (infusion site) and systemic (subjective and quantitative) reactions, will be captured on the appropriate data collection form and in the eCRF. Information to be collected for AEs includes event description, date of onset, assessment of severity, relationship to the IP and alternate etiology (assessed only by those with the training and authority to make a diagnosis and listed on Form FDA 1572 as an Investigator), date of resolution, seriousness, and outcome. Adverse events occurring during the study collection and reporting period will be documented appropriately regardless of relationship. Adverse events will be followed through resolution.

Any medical condition that is present at the time that the subject is screened will be considered as baseline and not reported as an AE. However, if the severity of any pre-existing medical condition increases, it will be recorded as an AE.

8.1.1.1 Adverse Events Grading

All AEs (laboratory and clinical symptoms) will be graded for severity and assessed for relationship to the IP (see definitions below). Adverse events characterized as intermittent require documentation of onset and duration of each episode. The start and stop date of each reported AE will be recorded on the appropriate data collection form and eCRF. Changes in the severity of an AE will be documented to allow an assessment of the duration of the event at each level of intensity.

Severity of Event: Adverse events will be assessed by the Investigator using a protocol-defined grading system (toxicity table included in Section 17.2). For events not included in the protocol-defined grading system, the following guidelines will be used to quantify severity:

- Mild (Grade 1): Events that are transient and may require only minimal or no treatment or therapeutic intervention and do not interfere with the subject's usual activities of daily living.
- Moderate (Grade 2): Events that are alleviated with additional specific therapeutic intervention. The event interferes with usual activities of daily living, causing discomfort but poses no significant or permanent risk of harm to the subject.
- Severe (Grade 3): Events interrupt usual activities of daily living, or significantly affects clinical status, or may require intensive therapeutic intervention. Severe events are usually incapacitating.

Relationship to Investigational Product: The assessment of the AE's relationship to the IP will be done by the licensed study physician indicated on Form FDA 1572 and the assessment will be part of the documentation process. Whether the AE is related or not, is not a factor in determining what is or is not reported in this study. If there is any doubt as to whether a clinical observation is an AE, the event should be reported.

In a clinical trial, the IP must always be suspect. The relationship to the IP will be assessed for AEs using the terms related or not related:

- Related There is a reasonable possibility that the IP caused the AE. Reasonable possibility means that there is evidence to suggest a causal relationship between the IP and the AE.
- Not Related There is not a reasonable possibility that the administration of the IP caused the event.

8.1.2 Serious Adverse Events

An AE or suspected adverse reaction is considered an SAE if, in the view of either the Investigator or Sponsor, it results in any of the following outcomes:

- Death
- A life-threatening AE¹

- Inpatient hospitalization or prolongation of existing hospitalization
- A persistent or significant incapacity or substantial disruption of the ability to conduct normal life functions, or
- A congenital anomaly/birth defect.

Important medical events that may not result in death, be life-threatening, or require hospitalizations may be considered serious when, based upon appropriate medical judgment, they may jeopardize the subject and may require medical or surgical intervention to prevent one of the outcomes listed in this definition. Examples of such medical events include, but are not limited to, allergic bronchospasm requiring intensive treatment in an emergency room or at home, blood dyscrasias or convulsions that do not result in inpatient hospitalization, or the development of drug dependency or drug abuse.

¹An AE or suspected adverse reaction is considered "life-threatening" if, in the view of either the Investigator or Sponsor, its occurrence places the subject at immediate risk of death. It does not include an AE or suspected adverse reaction that, had it occurred in a more severe form, might have caused death.

Serious AEs will be:

- Assessed for severity and relationship to the IP and alternate etiology (if not related to the IP) by a licensed study physician listed on Form FDA 1572 or by the Investigator or subinvestigator.
- Recorded on the appropriate SAE data collection form and in the eCRF.
- Followed through resolution by a licensed study physician (a physician listed on Form FDA 1572 as the Investigator or subinvestigator).
- Reviewed and evaluated by the SRC, the safety monitoring committee (SMC) (if related), and the IRB.

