8.6.3 Study Halting Criteria

Study dosing must be stopped, and a review of available safety data will be conducted by the SMC if any of the following occur:

- Death of a dosed subject following infusion and prior to the subject's last follow-up visit that was not the result of trauma or accident, regardless of relatedness to the IP.
- Occurrence of a life-threatening allergic/hypersensitivity reaction (eg, anaphylaxis) in any subject, manifested by bronchospasm with or without urticaria, or angioedema requiring hemodynamic support with pressor medications or mechanical ventilation.
- One subject with an IP-related SAE of any grade.
- Two or more subjects with a Grade 3 AE in the same system organ class (systemic toxicity, clinical laboratory tests, or vital sign measurements) considered related to the IP, except scenarios where there are acceptable physiological explanations for a Grade 3 abnormality (eg, Grade 3 hematuria in a menstruating female).
- One or more subjects experience a confirmed Grade 3 QTcF (≥500 msec or increase ≥60 msec), or 2 or more subjects cumulatively have experienced a Grade 2 change in QTcF (≥480 msec).

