8.7 Safety Oversight

8.7.1 Safety Review Committee

The SRC is composed of the DMID Medical Monitor, Sponsor Medical Monitor, and the Investigator at the clinical site. Objective dose escalation criteria and safety evaluations will be utilized. The Investigator will evaluate safety data from the sentinel group and notify the Sponsor Representative of intent to proceed if no study halting criteria (Section 8.6.3) are met. The SRC will evaluate the safety data through Day 8 for each cohort to determine whether dose escalation

can occur. These reviews do not necessitate formal meetings. The SRC will inform the Sponsor Representative that the study can proceed to begin dosing the next cohort if none of the events described in the study halting criteria (Section 8.6.3) or dose escalation criteria (Section 8.2.2) are met.

Should any of the study halting criteria or dose escalation halting criteria be met, the SMC will meet to evaluate the data and recommend appropriateness of further dosing. The decision to advance to the next dosing cohort will be documented and provided to the SRC and Sponsor Representative.

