8.7.2 Safety Monitoring Committee

The SMC is an independent group of experts (at least 3 members) that monitor subject safety and advises the Sponsor. The SMC members will be separate and independent of study personnel participating in this study and should not have scientific, financial, or other conflicts of interest related to the study. The SMC will consist of members with appropriate expertise to contribute to the interpretation of the data from this trial. A quorum will consist of a simple majority.

The SMC will review all available safety data during all scheduled ad hoc meetings:

- When study halting criteria or dose escalation criteria are met.
- At the request of the Sponsor to review a potential safety concern identified by the Investigator, Sponsor Medical Monitor, or DMID Medical Monitor.
- When an SAE occurs.

Procedures for the SMC reviews and meetings will be defined in the SMC charter. The SMC will review applicable aggregate data including, but not limited to, enrollment, demographics, dosing, laboratory, and safety data at scheduled time points during the study as defined in the charter. The SMC may request to receive data by AV-1 versus placebo in a closed session. The SMC may also request that the blind be broken for individual subjects, as needed, to assess safety issues. The SMC will make a recommendation to the Sponsor Representative in writing to continue, modify, or terminate the study as an outcome of each review or meeting.

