10.3.1 Randomization Procedures

This is a double-blind study. Neither the subjects, the Investigator, nor the Sponsor will be aware of the treatment assignment. Subjects will be randomly assigned to receive AV-1 or placebo in a 6:2 randomization ratio. Access to the randomization code will be strictly controlled according to the standard operating procedures of PPD.

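### Protocol Sections 8.1.2 and 8.7.2 set different triggers for SMC review of an SAE, so a single SAE judged not related has no one clear rule

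*Protocol*

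**What the plan says.** Section 8.1.2 of the protocol closes with a list of what happens to every SAE. Its last item is that SAEs will be "Reviewed and evaluated by the SRC, the safety monitoring committee (SMC) (if related), and the IRB". The condition in parentheses attaches to the SMC alone. The SRC and the IRB review the event either way.

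Section 8.7.2 lists the occasions on which the SMC reviews all available safety data. One of them is "When an SAE occurs", without any condition on causality.

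Two further provisions bear on the point. Section 8.1.2 has severity and relationship assessed "by a licensed study physician listed on Form FDA 1572 or by the Investigator or subinvestigator". Among the dosing stops in Section 8.6.3 that lead to SMC review is "One subject with an IP-related SAE of any grade".

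The SAP does not mention SMC review. Its section on interim analysis refers only to blinded review by the investigators, the medical monitor and the Sponsor's representative.

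**The concern.** The two provisions are both current, and they give different answers for an SAE that the site calls not related. Someone working from Section 8.1.2 would not expect the SMC to look at it. Someone working from Section 8.7.2 would convene the SMC.

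This matters because of who makes the causality call and who would check it. The call is binary (related or not related, Section 8.1.1.1) and is made at the site. Section 10.3.1 states: "Neither the subjects, the Investigator, nor the Sponsor will be aware of the treatment assignment". The SRC does not stand apart from that call, since Section 8.7.1 says: "The SRC is composed of the DMID Medical Monitor, Sponsor Medical Monitor, and the Investigator at the clinical site". The SMC does stand apart. Section 8.7.2 says: "The SMC is an independent group of experts (at least 3 members) that monitor subject safety and advises the Sponsor". It also lets the SMC ask for data split by AV-1 and placebo and for individual subjects to be unblinded. The narrower trigger therefore withholds event-triggered review from the committee best equipped to test the attribution. AV-1 has not been given to humans before (Section 2.2.1), so there is no clinical experience to guide the judgement.

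**Working it through.** No arithmetic applies, and the plan states no figure to reproduce. The check is to take each kind of SAE and follow both rules to the end.

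| Kind of SAE | Under Section 8.1.2 | Under Section 8.7.2 | Other route to the SMC |
|---|---|---|---|
| (a) Judged related | SMC reviews | SMC reviews | Section 8.6.3, related-SAE stop |
| (b) Judged not related, but meets a criterion that ignores causality | Not sent by this section | SMC reviews | Section 8.6.3 or 8.6.1, see below |
| (c) Any other single SAE judged not related | Not sent by this section | SMC reviews | None that is triggered by the event and mandatory |

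**Class (a).** The sections agree.

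**Class (b).** The criteria that bring an event to the SMC whatever its causality are:

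- a death "that was not the result of trauma or accident, regardless of relatedness to the IP" (Section 8.6.3);
- a life-threatening hypersensitivity reaction (Section 8.6.3);
- the QTcF criteria (Section 8.6.3);
- Grade 3 AEs in at least two subjects of one cohort under the same high-level term (Section 8.6.1).

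The sections differ in wording here, but the outcome is the same.

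**Class (c).** A hospitalization called not related is the plain example. Section 8.7.2 requires SMC review and Section 8.1.2 does not. The remaining halting criteria do not help. The related-SAE stop, the Grade 3 rule by system organ class (Section 8.6.3) and the Grade 2 rule (Section 8.6.1) all need a related event. The causality-free Grade 3 rule needs a second subject. Under Section 8.7.1 the SRC may clear the next cohort when no halting or escalation criterion is met, so one such event does not by itself bring in the SMC before escalation.

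**Can the two provisions be read together?** Only by giving the parenthesis in Section 8.1.2 no effect, or by reading a relatedness condition into Section 8.7.2. The protocol writes that condition out where it wants it, as in Section 8.6.3, so its absence from Section 8.7.2 cannot be assumed to be an oversight. No order of precedence is stated.

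**The case against.** The strongest case on the other side is that this is a wording mismatch with little practical effect. It has several parts.

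- **Section 8.1.2 does not forbid SMC review of an unrelated SAE.** Section 8.7.2 is the section that governs the SMC, and following it removes the problem. The charter, which is not among the documents, may also settle the matter. This stands as far as it goes, but the protocol would still give its users two rules.
- **The event is seen by others.** Under Section 8.3.1 every SAE goes to the contract research organization's safety group within 24 hours and then to the DMID pharmacovigilance group. The Sponsor's medical monitor and others are notified and assess its effect on subject safety. None of this depends on causality. The SRC includes two medical monitors besides the Investigator, and the IRB reviews every SAE. Section 8.2.2 has clinically significant results discussed with the Sponsor before escalation. Section 10.3.3 permits unblinding for an SAE. All of this stands.
- **The SMC has other ways in.** The Sponsor may ask it to review a concern, and it reviews aggregate data at times set by the charter. These are real backstops, but the first is discretionary and the second is not prompted by the event.

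A reader might infer that an SAE called not related would escape every independent check. The documents do not support that: the IRB sees every SAE, and the pharmacovigilance chain does not depend on causality. Nor does any section have the site send SAEs to the SMC itself, so the point concerns the committee's trigger and not the site's reporting duty. A reader might also infer that most SAEs would miss the SMC. The documents give neither an expected SAE count nor a split by causality, so no such proportion can be derived.

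**Conclusion.** The contradiction is real and lies in current operative text, but it is narrow. It reaches class (c) only: a single SAE judged not related that meets no other halting or escalation-halting criterion. For that class, following Section 8.1.2 makes event-triggered review by the only safety committee described as independent of study personnel depend on one blinded causality call at the site. Following Section 8.7.2 does not.

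The size is a class of events and not a number. If no such SAE occurs, nothing is lost. If one occurs, the study has no single rule for it. The conclusion assumes that the charter, which cannot be seen here, does not already override Section 8.1.2; even if it does, the protocol text still conflicts.

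The point does not extend to the dosing-stop rule in Section 8.6.3. That rule answers a different question and is not called into doubt here. Given the backstops, this is a correction that should be made for a first-in-human escalation, and not a sign that safety oversight is absent.

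**What to change.** Reconcile the two sections so that one trigger governs SMC review of an SAE. The simplest way is to delete the two words in parentheses, (if related), from the last item in Section 8.1.2. It then matches Section 8.7.2, the section that sets out the SMC's remit. Put the same trigger in the SMC charter. Section 8.6.3 needs no change.

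If the Sponsor in fact intends a related-only trigger, Section 8.7.2 and the charter would have to say so. Class (c) would then rest on Sponsor request and scheduled review, and the protocol should acknowledge that.

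The deletion costs a two-word amendment, a line in the charter and possibly a few additional ad hoc SMC reviews. It changes no analysis and no data collection.
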